9.2 Determination of subjective measurement of oral mucositis

The subjective measurement of oral mucositis will be obtained through patient self-assessment of mucositis using the Common Terminology Criteria for Adverse Events (CTCAE) Version 4.0 pain scales in person at visit 1 and between each site visit. Subjects will be instructed to say where on the scale they would assess their mucositis level and providers will complete the form. The Subject Self-Assessment Tool is attached as Appendix C.

9.3 Determination of pain associated with oral mucositis

This subjective measurement will be obtained through patient self-assessment of pain scales in person at the baseline visit and independently between each site visit. Subjects will be instructed to say where on the scale they would assess their pain level and providers will complete the form. The Subject Self-Assessment Tool is attached as Appendix C.

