2. Objectives/Endpoints

The primary objective of this Phase I/II study is to determine the maximum tolerated dose (MTD) of oral curcumin in patients who have chemotherapy-induced mucositis. The secondary objectives of this study are to determine whether oral curcumin:

- Decreases an objective measurement of oral mucositis
- Decreases the pain associated with oral mucositis
- Decreases the duration of mucositis
- Has an acceptable safety profile.

3. Study Design

This is a phase I/II study involving 2 parts: a dose escalation part and an expansion at the maximum tolerated dose.

In the first part, there will be 3 subjects at each dose level of curcumin (see table below). The doses will be taken 3 times each day for 14 days. Each dose will be taken as a mouth rinse containing curcumin and water, 3 times each day for 14 days. The mouth rinse will be used for 30 seconds and then swallowed. Subjects will be evaluated for dose-limiting toxicity (DLT, defined in section 6.1). The maximum tolerated dose (MTD, defined in section 2) will be determined. Subjects may participate in the study at a higher dose level, after they have completed the study at the current dose level and if they are eligible.

# Subjects	Curcumin/dose (gram)	Curcumin/day (gram)
3	0.33	1
3	1.0	3
3	2.0	6
3	3.0	9

In the second part of the study, there will be 23 subjects enrolled to an experimental (curcumin) arm and 23 subjects enrolled to a control (standard of care) arm. Subjects will be randomized to take a mouth rinse with or without the MTD of curcumin, 3 times each day for 14 days. The rinses will be swallowed. Subjects will be evaluated for response and toxicity. Subjects in the first part of the study may participate in the second part of the study, if they are eligible.

In both parts of the study, if the mucositis score \leq Grade 2 but is unresolved after 14 days of taking the study mouth rinse (curcumin or control), then the subject will

continue to receive the study mouth rinse until the mucositis is resolved (Grade 0).

This study will involve 12 subjects in the first part, plus an additional 3 subjects if a dose-limiting toxicity occurs (see section 2) and 46 subjects in the second part for a total of 61 subjects. This study is expected to take 2 years to complete enrollment, treatment and follow-up (6 months for the first part and 18 months for the second part).

4. Subject Selection

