5.1.1 Visit 1 (Screening)

Subjects will be asked to sign a consent form. An oral exam will be conducted to ensure good oral hygiene. A blood or urine sample will be collected for pregnancy testing, if applicable. A blood sample will be collected to assess liver function (CMP) and clotting function (PT and INR). A mucositis assessment (CTAE version 4.0 and WHO Oral Toxicity Scale) will be conducted and documented by a health provider (Appendix B). This visit will take approximately one hour.

5.1.2 Visit 2

5.1.3 THIS VISIT MUST OCCUR WITHIN 48 HOURS AFTER THE SCREENING VISIT. IF VISIT 2 OCCURS ON A DIFFERENT DAY THAN VISIT 1, ANOTHER MUCOSITIS ASSESSMENT (CTAE VERSION 4.0 AND WHO ORAL TOXICITY SCALE) WILL BE CONDUCTED AND DOCUMENTED BY A HEALTH PROVIDER (APPENDIX B) AND WILL BE CONSIDERED THE BASELINE ASSESSMENT. THE PROVIDER WILL ALSO ASK THE SUBJECT TO COMPLETE A SUBJECT SELF-ASSESSMENT (APPENDIX C). SUFFICIENT MOUTH RINSE WILL BE GIVEN TO THE SUBJECT FOR THE FIRST WEEK OF THE STUDY. THE DAILY LOG (APPENDIX A) AND THE PATIENT SELF-ASSESSMENT TOOL (APPENDIX C) WILL BE GIVEN TO THE SUBJECT. THE SUBJECT WILL BE ASKED TO COMPLETE THE LOG EVERY DAY UNTIL VISIT 3. THE SUBJECT WILL BE ASKED TO COMPLETE THE SELF-ASSESSMENT TOOL ON DAY 3 OR 4 AFTER THE FIRST DAY OF TAKING THE MOUTH RINSE. A BLOOD AND SALIVA SAMPLE WILL BE OBTAINED FOR RESEARCH PURPOSES (SECTION 10). THIS VISIT WILL TAKE APPROXIMATELY 30 MINUTES.Phone call 1

On day 3 or 4 after the first day of taking the mouth rinse for the study, the subject will be called by a study staff member, who will review and follow up on any side-effects that the subject is experiencing and answer any questions about the study or study mouth rinse. The staff member will remind the subject to complete a subject self-assessment tool (Appendix C) and the daily log (Appendix A) and bring them to the next visit. The phone call will take about 15 minutes.

5.1.4 Visit 3

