This visit will occur 7 days (+/- 1 day) after Visit 2. A mucositis assessment (CTAE version 4.0 and WHO Oral Toxicity Scale) will be conducted and documented by a health provider (Appendix B), who will also review and follow up on any side-effects that the subject is experiencing and check the daily log (Appendix A) to ensure that the subject is complying with the study. Sufficient mouth rinse will be given to the subject for the second week of the study. A blood sample will be obtained to assess liver function (CMP) and clotting function (PT and INR). A blood and saliva sample will be obtained for research purposes (section 10). This visit will take approximately 30 minutes.

5.1.5 Phone call 2

On day 10 or 11 after the first day of taking the mouth rinse for the study, the subject will be called by a study staff member, who will review and follow up on any side-effects that the subject is experiencing and answer any questions about the study or study mouth rinse. The staff member will remind the subject to complete a subject self-assessment tool (Appendix C) and the daily log (Appendix A) and bring them to the next visit. The phone call will take about 15 minutes.

5.1.6 Visit 4

This visit will occur 7 days (+/- 1 day) after Visit 3. A mucositis assessment (CTAE version 4.0 and WHO Oral Toxicity Scale) will be conducted and documented by a health provider (Appendix B), who will review and follow up on any side-effects that the subject is experiencing and obtain the daily log (Appendix A) from the subject. A blood sample will be obtained to assess liver function (CMP) and clotting function (PT and INR). A blood and saliva sample will be obtained for research purposes (section 10). If the mucositis score \leq Grade 2 but is unresolved, then the subject will continue to receive the study mouth rinse (curcumin or standard mouth rinse) until the mucositis is resolved (Grade 0). Sufficient mouth rinse will be given to the subject for the subsequent week of the study. This visit will take approximately 30 minutes.

5.1.7 Phone call 3

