On day 17 or 18 after the first day of taking the mouth rinse for the study, the subject will be called by a study staff member, who will review and follow up on any side-effects that the subject is experiencing and answer any questions about the study or study mouth rinse. The staff member will remind the subject to complete a subject self-assessment tool (Appendix C) and the daily log (Appendix A) (only if they are still on study mouth rinse) and bring them to the next visit. The phone call will take about 15 minutes.

5.1.8 Visit 5

This visit will occur 7 days (+/- 1 day) after Visit 4. A mucositis assessment (CTAE version 4.0 and WHO Oral Toxicity Scale) will be conducted and documented by a health provider (Appendix B), who will review and follow up on any side-effects that the subject is experiencing and obtain the daily log (Appendix A) from the subject (if the subject is still on study mouth rinse). A blood sample will be obtained to assess liver function (CMP) and clotting function (PT and INR). A blood and saliva sample will be obtained for research purposes (section 10). If the mucositis score \leq Grade 2 but is unresolved, then the subject will continue to receive the study treatment (curcumin or standard mouth rinse) until the mucositis is resolved (Grade 0). Sufficient mouth rinse will be given to the subject for the subsequent week of the study. This visit will take approximately 30 minutes.

5.1.9 Weekly phone calls to subjects receiving study mouth rinse (curcumin or standard mouth rinse)

Between each visit, each subject will be called by a study staff member, who will review and follow up on any side-effects that the subject is experiencing and answer any questions about the study or study mouth rinse. The staff member will remind the subject to complete a subject self-assessment tool (Appendix C) and the daily log (Appendix A) and bring them to the next visit. The phone call will take about 15 minutes.

5.1.10 Weekly visits for subjects receiving study mouth rinse (curcumin or standard mouth rinse)

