5.2 Study Calendar

Study Procedure	Visit 1 (Screening)	Week 1		Week 2		Week 3		Week 4- mucositis resolution		Final visit
	day -1	Visit 2: day 0	Phone call 1: day 3	Visit 3: day 7	Phone call 2: day 10	Visit 4: day 14	Phone call 3: day 17	Visit: For phase II: weekly cycle repeated until mucositis is resolved (and no AEs)	Phone calls	
activity window		At or w/in 48hr of Visit 1	+ 1 day	+/- 1 day	+ 1 day	+/- 1 day	+ 1 day	+/- 1 day	+ 1 day	+/- 1 day
Sign Informed Consent	X									
Oral exam for hygiene	X									
Pregnancy test	X ¹									
Provider mucositis assessment ²	X	X ³		X		X		X ^a		X
Provider supplies study mouth rinse		X		X		X ^a		X ^a		X
Provider supplies study journal, self-assessment		X		X		X ^a		X ^a		X
Provider collects journal and self-assessments				X		X		X ^a		X
Remind subject to complete self-assessment		X	X		X		X		X ^a	
Blood collection for liver function (CMP) ⁴	X			X		X		X ^a		X
Blood collection for clotting (PT and INR) ⁴	X			X		X		X ^a		X
Research blood collection ⁵		X		X		X		X ^a		
Research saliva collection ⁵		X		X		X		X ^a		
Collect AEs			X	X	X	X	X	X ^a	X ^a	X
Review of concomitant medications	X	X		X		X		X ^a		X

¹ Blood or urine pregnancy test, if not already done as part of standard of care

² Includes CTAE version 4.0 and WHO oral Toxicity scale.

³ Mucositis assessment at Visit 2, only if a different day than Visit 1 (does not need to be repeated if Visit 1 and 2 are done on the same day)

⁴ Does not need to be repeated if already done for standard of care.

⁵ 6 ml of peripheral blood into a non-anti-coagulated tube, 2 ml saliva into a sterile tube; processed and stored as described in the operations manual.

^a Only if subject is still taking study mouth rinse based on improvement of mucositis at each visit, beginning at visit 4.

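### Pain is a secondary efficacy objective, but no pain score is scheduled at day 7 or day 14, the documents disagree on who is scored at day 17–18, and from week 4 only subjects still on rinse are scored

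*Combined protocol and SAP*

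**What the plan says.** Section 2 lists among the secondary objectives to determine whether curcumin "Decreases the pain associated with oral mucositis". Section 9.3 obtains pain by self-assessment on Appendix C, "in person at the baseline visit and independently between each site visit".

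Section 5.1 gives the days. The form is completed at Visit 2. Subjects are then asked to "COMPLETE THE SELF-ASSESSMENT TOOL ON DAY 3 OR 4 AFTER THE FIRST DAY OF TAKING THE MOUTH RINSE". The next form goes with phone call 2 (section 5.1.5: "On day 10 or 11 after the first day of taking the mouth rinse for the study, the subject will be called"), and the one after that with phone call 3 on day 17 or 18. For that last call, the reminder in section 5.1.7 reads: "complete a subject self-assessment tool (Appendix C) and the daily log (Appendix A) (only if they are still on study mouth rinse".

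Calendar footnote a (section 5.2) marks items done "Only if subject is still taking study mouth rinse based on improvement of mucositis at each visit, beginning at visit 4". Section 9.2, on self-assessed mucositis, places the self-assessment "in person at visit 1 and between each site visit". Sections 9.2 and 9.3 say providers fill in the form. The phone-call sections have the subject complete it and bring it to the next visit.

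**The concern.** The randomised part gives a 14-day course, and mucositis is graded by a provider at day 7 and day 14. Pain is not self-scored on either day. Pain at the end of the course, a natural reading of whether the rinse relieves pain, therefore has no measurement, and no score after baseline falls on the same day as a provider grade.

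After day 14, who remains on rinse depends on outcome. Subjects at grade 0 stop, those unresolved at grade 2 or lower continue, and section 6.2 removes those with no improvement. Pain data restricted to subjects still on rinse leave out those who healed, in whom an effective rinse did its work, and also those removed. Comparing the arms in what is left would not be a randomised comparison. No section names a pain time point or specifies the pain analysis beyond the generic tests in section 9, so nothing in the plan rules such a comparison out.

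**Working it through.** **The plan's own figure.** Section 8 states 91% power with 23 per arm, a standard deviation of the means of 0.50 and a within-group SD of 1.00. The noncentrality is 46 × (0.50/1.00)² = 11.5 with 1 and 44 degrees of freedom. This gives power 0.912, so the figure reproduces. It applies to the provider's mucositis score; no power is given for pain.

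**Schedule of the self-assessment form.**

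| Day | Contact | Section 5.1 | Calendar reminder row | Calendar form-supply row |
|---|---|---|---|---|
| 0 | Visit 2 | form completed | X | X |
| 3–4 | Call 1 | reminder to complete | X | – |
| 7 | Visit 3 | provider grade, no self-score | blank | X |
| 10–11 | Call 2 | reminder to complete | X | – |
| 14 | Visit 4 | provider grade, no self-score | blank | X, footnote a |
| 17–18 | Call 3 | reminder; rinse condition follows the daily log | X, unmarked | – |
| Week 4 on | Weekly calls and visits | for subjects receiving rinse | X, footnote a | X, footnote a |

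At day 7 and day 14 the calendar has forms collected, not completed. At day 17–18 the unmarked reminder points to all subjects. So does the parenthesis in 5.1.7, which follows the daily log; section 5.1.8 attaches the same condition to the log alone. The day-14 supply cell points to subjects still on rinse. Taken together, a healed subject could be reminded to complete a form that was not supplied.

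**Precision from more scores.** Assume equal variances and one correlation r between every pair of scores, baseline included. The variance of the baseline-adjusted mean of k scores is then proportional to (1 + (k − 1)r)/k − r².

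| r | k = 1 | k = 2 (current) | k = 4 | Cut from 2 to 4 |
|---|---|---|---|---|
| 0.3 | 0.91 | 0.56 | 0.385 | 31% |
| 0.5 | 0.75 | 0.50 | 0.375 | 25% |
| 0.7 | 0.51 | 0.36 | 0.285 | 21% |

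For example, at r = 0.5 and k = 4: (1 + 1.5)/4 − 0.25 = 0.375. A single Visit 4 score (k = 1) has more variance than the mean of the two scores already scheduled: 0.91/0.56 = 1.63, 0.75/0.50 = 1.50 and 0.51/0.36 = 1.42, so 42% to 63% more.

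**Selection where only subjects on rinse are scored (illustration).** Assume latent severity is normal with SD 1, mean 1.0 on control and 0.5 on curcumin, healed if below 0.5, with pain equal to severity floored at 0. Healed proportions are then 31% and 50%.

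- All subjects: mean pain is 1.0 × 0.841 + 0.242 = 1.083 on control and 0.5 × 0.691 + 0.352 = 0.698 on curcumin, a difference of about 0.385.
- Unhealed only: 1.0 + 0.352/0.691 = 1.509 and 0.5 + 0.399/0.5 = 1.298, a difference of 0.211, about 55% of the full one.

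Without the floor, and over assumed resolution of 50–70% on curcumin and 20–50% on control, the difference among the unresolved is 31% to 46% of the full one wherever the arms differ (for example 0.84 SD becomes 0.39 SD at 50% against 20%, and 0.52 SD becomes 0.16 SD at 70% against 50%). Between 7 and 12 curcumin and 12 and 18 control subjects would remain, and power for a 1.0 SD difference would fall from 91% to between 51% and 74%. The one anchor in the documents is section 6.3, which stops the study if fewer than 5 of the first 10 curcumin subjects are at grade 0 at Visit 4.

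**The case against.** Pain is a secondary objective behind the MTD, and the objective names no time point, so day 14 is a reviewer's choice. Pain is scored in both treatment weeks, in both arms, against an in-person baseline. That is a valid randomised on-treatment comparison, and it needs no same-day provider grade. This stands. What is missing is the end-of-course value.

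A reader might infer that after day 14 pain is scored only in subjects still on rinse, so that day 10–11 is the last score every subject can have. The documents do not establish this for day 17–18, where they conflict.

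A reader might also infer that the plan's own pain analysis is selected on outcome. No pain comparison after day 14 is planned: the week-by-week ANOVA in section 8 is described for the provider's scales. The selection figures describe a possible analysis, and only where scoring is restricted.

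Appendices B and C are not in the text available for this review, so a pain item on the provider form cannot be excluded. Section 11 lists a pain scale among the data without timing. The calendar's final-visit column has unmarked supply and collection of forms, but no reminder. That column carries no fixed study day, so it would not supply the missing day-14 score.

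The baseline conflict is mild. Section 9.3 and the Visit 2 procedures agree; only section 9.2, on self-assessed mucositis, says Visit 1, and the two visits may fall on one day.

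**Conclusion.** The point holds in a limited form. The available text schedules no self-assessed pain score at day 7 or day 14, and the last score within the course is day 10–11. Day 17–18 is contradictory on who is scored. From week 4, scoring is confined to a group selected on mucositis outcome. The existing day 3–4 and day 10–11 scores support a randomised comparison, so the objective can still be assessed, only without an end-of-treatment value.

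Adding the two site-visit scores would cut the variance of the adjusted mean by 21% to 31%, assuming a common within-subject correlation between 0.7 and 0.3. The shrinkage from about 0.38 to 0.21 is illustrative: it rests on assumed healing rates and a floor on pain, and says nothing about a comparison in all randomised subjects. This is a worthwhile, inexpensive improvement; it does not invalidate the trial.

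**What to change.** - Have every randomised subject complete Appendix C at Visit 2 (baseline), Visit 3, Visit 4 and Visit 5, whether or not still on rinse, and keep the day 3–4 and day 10–11 scores. This concerns data collection only; section 6.2 should say whether subjects removed under it still give these scores.
- Make the between-arm pain comparison the baseline-adjusted mean, or a repeated-measures model, over the four on-treatment scores (day 3–4, 7, 10–11 and 14). Report the Visit 4 contrast as the end-of-treatment effect. Do not rest the comparison on Visit 4 alone, which is less precise than the two-score mean already available.
- State that no between-arm pain comparison will be based on subjects still on rinse.
- Reconcile sections 9.2, 9.3, 5.1 and calendar footnote a on the baseline visit, on who completes the form, and on who is scored at day 17–18.

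The cost is protocol wording and a few minutes of subject time at visits that already take place.

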9.4 Determination of the duration of mucositis

The healing time will be calculated using the health provider's assessment of mucositis (CTCAE and WHO scales) by determining the number of days between study mouth rinse initiation and the day on which grade 0 is achieved.

9.5 Determination of toxicity profile

Toxicities will be graded by health care providers using the Common Terminology Criteria for Adverse Events (CTCAE) Version 4.0. A baseline evaluation will occur prior to study mouth rinse administration, and then weekly during study mouth rinse administration. Data will be recorded and entered into a database.

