4.2 Exclusion Criteria

- Current use of therapeutic doses of anticoagulants such as warfarin or antiplatelet agents (prophylactic doses and agents are acceptable)
- Biliary tract obstruction or cholelithiasis
- History of gastric or duodenal ulcers or hyperacidity syndromes
- AST or ALT $>$ 2 x ULN
- Total bilirubin \geq 2 x ULN
- INR $>$ 1.5
- Previous stem cell transplant (allogeneic or autologous)
- Preexisting oral disease, such as active oral infection, trauma to the oral mucosa or oral ulceration prior to chemotherapy
- Known allergy/hypersensitivity to curcumin, yellow food colorings, or other members of the Zingiberaceae (ginger) family
- Pregnant or breastfeeding

Potential subjects are identified by medical record review. Eligible subjects are asked to give their written consent to participate in this study. The tests required to screen subjects for this study include a pregnancy test, INR and CMP.

5. Study Procedures and Schedule

The study mouth rinse will be initiated when subjects have $>$ grade 2 mucositis, which could be at any point during their chemotherapy cycle. Subjects who develop $>$ grade 2 mucositis will receive appropriate adjustments in their chemotherapy dose to reduce toxicity with subsequent cycles.

In the first part, there will be 3 subjects at each dose level of curcumin. Each dose will be given as a mouth rinse containing curcumin and water.

In the second part, subjects will be randomized to take a mouth rinse with the MTD of curcumin or a standard mouth rinse, 3 times each day for 14 days. The curcumin mouth rinse will be designated “study mouth rinse” to differentiate it from the standard mouth rinse.

All subjects will be instructed to rinse their mouths with the study or standard mouth rinse 3 times each day for 14 days. Subjects will be instructed to use the study or standard mouth rinse for 30 seconds and then swallow the rinse. Subjects will be instructed not to eat within one hour after using the study or standard mouth rinse. Subjects will be instructed to use a saline mouth rinse after eating any food to keep their mouth clean. A daily log (Appendix A) will be available for each subject and will include a checklist that will simplify the rinsing schedule as well as an area for the subject (or family member) to document mouth rinse administration. No other adjunctive topical treatment will be used during the study.

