5.6 Determination of MTD

The MTD will be determined as follows: If a DLT occurs in any one of the 3 patients at a specific dose level, an additional 3 patients must be treated at that dose level to achieve statistical validity of the MTD. If 2 of the 6 patients (17%) at a dose level develop a DLT, the previous dose level will be used as the MTD. If no DLT is observed, then the MTD will be the highest dose. To ensure safety of subjects at each dose level, all assessments will be completed at Visit 5 for subjects at a dose level before another subject is given study drug at the

subsequent dose level.

6. Expected Adverse Events

Toxicities will be graded by health care providers using the Common Terminology Criteria for Adverse Events (CTCAE) Version 4.0 weekly after initiation of study mouth rinse until mucositis is resolved (Grade 0) (see Provider Assessment in calendar, section 5.2). Toxicities will be assessed by subject self-evaluation during study mouth rinse administration between clinic visits (see Subject Assessment in calendar, section 5.2).

Very few studies have reported any severe or serious side effects from curcumin and most studies have involved oral administration of curcumin. No major toxicity has been found in studies where curcumin is used short-term. Increased bleeding may occur due to inhibition of platelet aggregation (very rare). Possible other side effects associated with curcumin include: vomiting, nausea, rash and GI distress. In a study of subjects with colon cancer, oral curcumin at doses ranging from 0.45 to 3.6 gram/day for 1 to 4 months was associated with nausea and diarrhea and caused an increase in serum alkaline phosphatase and lactate dehydrogenase[15]. In one study of patients with advanced pancreatic cancer, 5 of the 17 patients receiving oral curcumin (8 gram/day) in combination with gemcitabine reported intractable abdominal pain after a few days to 2 weeks of curcumin intake[16]. In a recent study of topical curcumin for mucositis in juveniles and children[14], there were no oral adverse events documented and no systemic adverse events that possibly could be related to the use of the curcumin mouthwash.

Patients will receive full supportive care as appropriate. The rationale for treatment, dosage and the date of treatment will be recorded in the medical record.

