This study will involve 12 subjects in the first part, plus an additional 3 subjects if a dose-limiting toxicity occurs (see section 2). This sample size is similar to other phase I dose escalation studies and will result in a determination of maximum-tolerated dose. The first objective for the second part (n=46) is to determine whether curcumin decreases an objective measurement of oral mucositis. Mucositis assessment will be conducted by the provider using the WHO scale and CTCAE scale. The scales are continuous between 0 and 4. Analysis of variance will be used to compare the two groups of subjects (standard mouth rinse versus study mouth rinse) separately for each time period (baseline and each week after study mouth rinse initiation). In a one-way ANOVA study, sample sizes of 23, and 23 are obtained from the 2 groups whose means are to be compared. The total sample of 46 subjects achieves 91% power to detect differences among the means versus the alternative of equal means using an F test with a 0.05 significance level. The size of the variation in the means is represented by their standard deviation which is 0.50. The common standard deviation within a group is assumed to be 1.00.

9. Measurement of Effect

Differences between the two mouth rinse groups will be studied with the chi-square test for categorical factors and the analysis of variance F-test for continuous variables with a 0.05 significance level.

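### After the first weeks, toxicity follow-up depends on healing, the sections disagree on when it ends, and no common window or exposure denominator is set for comparing the arms

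*Combined protocol and SAP*

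**What the plan says.** An acceptable safety profile is one of the four secondary objectives (Section 2), and Part 2 evaluates toxicity in both randomized arms of 23.

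Three places tie toxicity observation to healing or rinse use:

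- Section 9.5: "A baseline evaluation will occur prior to study mouth rinse administration, and then weekly during study mouth rinse administration".
- Section 6: grading is "weekly after initiation of study mouth rinse until mucositis is resolved (Grade 0").
- Section 5.2, footnote a, which marks adverse event collection at the visits and calls from week 4 on: "Only if subject is still taking study mouth rinse based on improvement of mucositis at each visit, beginning at visit 4".

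The rinse period has a fixed part and an open part. Section 5 fixes the first: "All subjects will be instructed to rinse their mouths with the study or standard mouth rinse 3 times each day for 14 days". Section 5.1.6 opens the second: if the score at Visit 4 is Grade 2 or lower but not resolved, "then the subject will continue to receive the study mouth rinse (curcumin or standard mouth rinse) until the mucositis is resolved (Grade 0"). Section 6.2 removes subjects whose mucositis has not improved after 14 days.

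Other places collect events regardless of rinse use. The calendar row for adverse events carries no footnote at either call or visit up to day 14, at phone call 3 (day 17) or at the final visit. Phone call 3 and Visit 5 (Sections 5.1.7 and 5.1.8) review side effects; the on-rinse condition there covers only the diary items. The calendar describes the later Phase II schedule as a "weekly cycle repeated until mucositis is resolved (and no AEs").

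On analysis, Section 9 states generally: "Differences between the two mouth rinse groups will be studied with the chi-square test for categorical factors". Section 9.6 makes a subject evaluable for safety after one dose. Section 9.5 names no toxicity endpoint, test, window or exposure adjustment.

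**The concern.** Duration of mucositis is an efficacy outcome (Section 9.4). If it also decides how long a subject is watched for toxicity, the proportion ever having a toxicity depends on healing as well as on risk. At the same weekly risk, an arm watched longer shows more subjects with an event.

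If curcumin heals faster and its subjects leave observation sooner, a real excess of toxicity could be diluted. If it heals more slowly, it could look more toxic than it is. With no window or denominator specified, the analyst would have to choose one after seeing the data.

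**Working it through.** **The plan's own figure.** The only stated operating figure is for efficacy: 91% power in Section 8. With noncentrality 46 × 0.50² / 1.00² = 11.5 and F(1, 44) at 0.05, power is 0.912, so it reproduces. It does not bear on toxicity, for which no figure is stated.

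**When does collection end?**

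- Section 6, read literally, ends grading at Grade 0, which could be Visit 3.
- Section 9.5 ends it with the rinse.
- The calendar runs to day 17 for everyone, then follows footnote a, then adds a final visit with no stated day.
- Section 5.1.8 reviews side effects at Visit 5 (about day 21). The calendar has no column for Visit 5; if it belongs to the week 4 column, footnote a makes it conditional.
- A subject who enters at Grade 2 and is still Grade 2 at Visit 4 meets both the continuation rule of Section 5.1.6 and the removal rule of Section 6.2. Those passages must be reconciled, because they decide who is observed further.

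**Size.** Inputs from the plan: 23 per arm, weekly visits, chi-square at 0.05. Assumed, because the documents give neither: healing times by arm (Weibull, shape 2) and a constant event rate of 0.15 per week.

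- Share unhealed at day t with median m: S(t) = exp(−ln 2 × (t/m)²).
- Observation L: the first weekly visit, from day 14 on, showing Grade 0, but never less than a floor of day 17 or day 21.
- P(event) = mean of 1 − exp(−0.15 × L/7).
- Rejection: exact enumeration of the Pearson chi-square (no continuity correction), 23 v 23.

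Example, median 10 days, day-17 floor: 74.3% are observed to day 17, 21.0% to day 21, 4.3% to day 28 and 0.4% to day 35. The event probabilities are 30.5%, 36.2%, 45.1% and 52.8%, so P = 0.227 + 0.076 + 0.019 + 0.002 = 0.324.

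Equal true risk in both arms:

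| Median healing, curcumin v control | Floor | Subjects with an event | Rejection |
|---|---|---|---|
| 10 v 10 | day 17 | 32% v 32% | 5% |
| 10 v 21 | day 17 | 32% v 43% | 11% |
| 10 v 28 | day 17 | 32% v 50% | 22% |
| 10 v 21 | day 21 | 37% v 44% | 8% |
| 10 v 28 | day 21 | 37% v 51% | 16% |
| 10 v 21, 30% of those unhealed at day 14 removed but seen to the floor | day 21 | 37% v 42% | 7% |

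In the 10 v 21 case with a day-17 floor, mean observation is 2.6 v 3.9 weeks. A simpler model agrees in order of size: 70% v 30% healed at day 14, later weekly healing 60% v 30%, weekly event risk 5% to 20% in both arms. With a day-21 floor the gap is 4.6 to 9.0 points and rejection 7.2% to 9.8%.

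**Masking.** Let the true weekly rate on curcumin be 50% higher (0.225 v 0.15). With healing at 10 v 21 days, the proportions are 44% v 43% with the day-17 floor and 50% v 44% with the day-21 floor. Over a fixed 14 days they are 1 − exp(−0.45) = 36% v 1 − exp(−0.30) = 26%.

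**Direction.** Suppose removal ends observation at day 14, healed subjects are seen to day 21, and, as an extreme, everyone unhealed at day 14 is removed. With medians 10 v 21, the shares healed at day 14 are 0.743 v 0.265. Then P = 0.743 × 0.362 + 0.257 × 0.259 = 34% on curcumin and 0.265 × 0.362 + 0.735 × 0.259 = 29% on control. The bias has reversed.

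**Fixed window.** To day 14 with equal risk, both arms show 26% and the test rejects in 5.1%.

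**The case against.** A reader might infer that toxicity is collected only while a subject is on the rinse. That matches the wording of Section 9.5 but not the whole document: day 17, Visit 5 and the final visit are not tied to rinse use, the Phase II cycle also waits for the absence of adverse events, and the first 14 days are a fixed rinse period in both arms. The documents disagree with one another; they do not uniformly stop at healing.

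A reader might also infer a planned chi-square test of toxicity. The sentence in Section 9 is general, and the safety objective could be answered descriptively. This stands. But no other between-arm method for categorical data is offered, and crude proportions set side by side carry the same bias without a test.

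Nor do the documents support the claim that an effective curcumin would necessarily look safer. Equal healing gives no bias, removal of non-improvers can offset or reverse it, and the healing and event rates above are assumptions. With 23 per arm, power for toxicity is low in any window.

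What remains is that no section sets a common window or denominator. A final visit without a date does not supply one, and continuing until there are no adverse events makes follow-up depend on the safety outcome too.

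**Conclusion.** The point holds in a limited form. Beyond the early common period, how long a subject is observed for toxicity depends on healing and on removal for non-improvement. The sections disagree on the end of collection, and nothing makes the arms comparable in time. A crude between-arm comparison can therefore be confounded with efficacy if healing differs.

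Under the assumed rate of 0.15 per week and healing at 10 v 21 days, the spurious gap is about 11 points with a day-17 floor and 7 points with a day-21 floor. It is smaller with removal of non-improvers, larger if healing differs more, and zero if healing is equal. The sign is not settled by the documents. This is a cheap improvement to a secondary objective; it does not affect the MTD objective or the efficacy power.

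**What to change.** 1. Reconcile Sections 5.1.7, 5.1.8, 5.2, 6 and 9.5 on when adverse event collection ends, including the day of the final visit and whether Visit 5 is conditional. Collection through day 14 should be stated as applying to every subject whether or not healed, as the calendar already shows; otherwise the window in item 2 is not complete.
2. In Section 9.5, name the toxicity endpoint and base any between-arm comparison on events with onset from first rinse to day 14 (Visit 4), in all subjects with at least one dose. Define the window by onset day, because the visits have a one-day tolerance.
3. Report all toxicity, including later events, per subject-week of observation by arm. Showing the rate to day 14 and after day 14 separately avoids relying on a constant risk over time.

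Cost: protocol and SAP wording and one extra table, with no added visits. Downside: events after day 14 leave the headline comparison, but they stay in the rate table and the listings.
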